## 5.1 Study Design

This will be an ***observational***, longitudinal case-crossover study nested within a cohort study, following up to 730 Veterans seen for LBP in VA primary care prospectively for 12 months. Study procedures will not make changes to nor in any way affect the typical medical care for LBP provided at VAPSHCS. **All study assessments following recruitment will be “e-Questionnaires” that participants complete using their own personal electronic devices (smartphones, tablets, or PCs, not provided by the study).** There are two types of e-Questionnaires that participants will complete: “*scheduled e-Questionnaires*” and “*flare window e-Questionnaires*”. Scheduled e-Questionnaires are quasi-random, ‘cue-elicited’ frequent assessments that will be repeated numerous times throughout the 1-year follow-up period. Cues to complete scheduled e-Questionnaires are automated “e-Alert” notifications sent by text message and email at the start of each “*scheduled assessment window*”, the 3-hour period during which a scheduled e-Questionnaire may be completed. ***Scheduled e-Questionnaires will occur three times each week during weeks 1-4 of follow-up, once a week during weeks 5-8, and twice a month during months 2-12.*** Participants will also complete unscheduled “*flare window e-Questionnaires*” on an *ad hoc* basis, if they experience new flares of LBP at any time during the 1-year follow-up period. At study entry, participants will receive training on how to complete flare window e-Questionnaires, if they experience flares of pain, by logging on to a secure Participant Portal (the **Flares of LBP with Activity Research Study** or “FLARES” website) within 3 hours after the onset of a new pain flare. In addition, all scheduled e-Questionnaires will remind participants to complete a flare window e-Questionnaire if they have a new pain flare. Scheduled e-Questionnaires and flare window e-Questionnaires generally contain the same question items, however, scheduled e-Questionnaires inquire about activity exposures *preceding the start of the scheduled assessment window* (when e-Alert notifications are sent), and flare window e-Questionnaires inquire about activity exposures *over the time period preceding the flare onset*. Each e-Questionnaire will begin by prompting the participant with the definition of a LBP flare. Participants will then report whether or not they are experiencing a flare, the primary outcome for Aim 1 of this study. E-Questionnaires will also inquire about activity exposures that have occurred over the 24-hour period prior to the assessment window start and - *if* an activity is reported – ask for further clarification of whether the activity was performed in the 2-hour period prior to the assessment window start. Further questions included in every e-Questionnaire are time-varying pain and psychological covariates (pain intensity, depression, catastrophizing, stress, etc.) assessed using brief, validated measures. All e-Questionnaires are inherently time lagged for activity-flare relationships, since they capture *current* flare status at time=t, and activities in the 24-hour period *before* the start of the assessment window/flare onset (t-1). Participants may also be offered to wear the optional ActiGraph wGT3X-BT unit continuously for weeks 1-4 of the study. Due to the participant burden involved with frequent serial e-Questionnaire assessments, a run-in period during weeks 1 and 2 of follow-up will exclude those individuals unable to maintain compliance with these assessments. Aim 1 analyses will examine the short-term effects of 10 specific activity categories on participant-reported flares across all study assessments over 1-year follow-up. Aim 2 analyses will examine associations between the frequency of exposure to 10 specific activity categories over weeks 1-4 of follow-up, and long-term functional recovery at 12 months as defined by the RMDQ. All analyses will use a biopsychosocial framework accounting for potential confounders (sociodemographics, psychological factors, etc.) and effect modifiers, and will include sensitivity analyses to examine the robustness of findings and important study assumptions.

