### 5.2.7 Payment to Participants

Participants will be compensated for the time taken to complete the informed consent process, and for completion of each e-Questionnaire. Compensation will be paid by check or by direct deposit (EFT). The amounts of compensation will include the following: \$20 for completion of informed consent procedures, \$12 for the baseline e-Questionnaire, \$7 each for scheduled e-Questionnaires (up to 36 for each participant), \$7 for the first 10 flare-period e-Questionnaires, \$4 for the 2nd set of 10 flare-period e-Questionnaires completed (that is, #11-20 completed), and \$2 for the 3rd set of 10 flare-period e-Questionnaires completed (that is, #21-30 completed). Participants will have the option to complete more than 30 flare-period e-Questionnaires if they wish, but the study will not compensate them for flare-period e-Questionnaires beyond the first 30. The decreasing payment for higher numbers of completed elective flare-period e-Questionnaires was specifically introduced to address a prior scientific reviewer suggestion (in the 1st round of formal peer review by RR&D) that the research processes employed reduce incentives for spurious flare over-reporting. There is also a \$15 compensation for the exit e-Questionnaire, and a \$30 incentive for return of the ActiGraph unit. A larger (\$50) incentive for ActiGraph return may be offered if an ActiGraph unit is not initially returned. This contingency plan for a higher compensation amount if the ActiGraph unit is not initially returned will not be disclosed to participants in the informed consent documents, since it would incentivize participants to delay returning the ActiGraph. This means that the amount listed for total possible compensation in the Information Statement document (\$459) is \$20 less than the amount listed for total possible compensation in the IRQ (\$479) and other documents in this human subject application. For participants not wearing ActiGraphs, the total study compensation will be up to \$429.

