**All other study evaluations as described immediately below will be conducted as part of the e-Questionnaires that are non-VA data collection. These are presented here for the sake of completeness, although their initial conduct/acquisition are not a part of the VA component of the research.** After acquisition as part of the non-VA component of this research, the data will be shared with the VA study team, and henceforth will become VA data. The baseline e-Questionnaire will be administered within 2 days of a participant completing informed consent. Scheduled e-questionnaires will be administered 3 times weekly during weeks 1-4, once a week during weeks 5-8, and twice a month from months 2-12. The exit e-Questionnaire will be administered at 1-year follow-up. Flare window e-Questionnaires are completed on an ad hoc basis during the 1-year follow-up period, and are participant-initiated (not on a set schedule)

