25% based on a previously conducted pilot study), (3) number of case/control periods, and (4) proportion of participants who are statistically informative (with both case and control periods). Given the transient nature of flares, in our view, only activity exposures with moderate magnitude effects (ORs of 1.5-2.0) will have a meaningful impact on the population level. Informed by the characteristics of activities, flares, and missing data from our pilot, we estimated power using simulated data with 1000 replications, assuming  $\alpha=0.005$  (Bonferroni-corrected for 10 activity groups), comparing different assumptions for sample size determinants, including activity frequencies as low as 3%. A sample size of  $n=440$  yielded  $\approx 90\%$  power to detect ORs of 1.5 for activity frequencies  $\approx 10\%$ , 80% power to detect OR=1.6 at activity frequency=5%, and 80% power for OR= 1.81 given activity frequencies as low as 3% (**Figure 2**). Allowing for 40% of participants not being analyzed due to having limited data available (loss to follow-up, fail run-in period, etc.), this yielded **a planned sample size of  $n=730$  for Aim 1**. These power estimates are highly conservative, since (1) they use data from scheduled e-Questionnaires only and assume no data from *ad hoc* flare-window e-Questionnaires, and (2) they assume no information at all from the  $n=290$  with limited data. Moreover, they are based on binary activity exposures, and analyses using continuous exposures (incorporating duration and frequency) will have greater power. As a point of comparison, the previously conducted pilot study was able to detect ORs  $\geq 2.5$  and  $p$ -values  $< 0.001$  despite having  $\sim 9x$  fewer participants than the currently proposed study. For Aim 2, using the same data simulated for Aim 1, and assuming an expected mean (standard deviation) 1-year RMDQ scores of 8.8 (6.4) from a prior study, Bonferroni-corrected  $\alpha=0.005$ , activity frequencies  $\approx 20\%$ , and  $n=440$  without missing data (from  $n=730$  initially recruited), we estimated power over a range of scenarios where we varied the strength of the association between the *change* in activity frequency over the 1st 4 weeks of follow-up (for each of the 10 activity categories) and a minimum clinically important change in 1-year RMDQ of 2.5 points. We found  $\geq 80\%$  power to detect a 2.5-RMDQ-point difference at 12 months in scenarios where a 65% change in activity frequency over the 1st 4 weeks produced a 2.5-RMDQ-point difference at 12 months, and in all scenarios where the activity frequency-RMDQ relationships was *more* extreme (e.g., if a smaller % change in activity frequency produced a 2.5-RMDQ-point difference at 12 months. This confirms adequate power with **a planned sample size of  $n=730$  for Aim 2**.

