**5.6.2 a. Aim 1 analyses:** We will examine associations between activity group exposures and the participant-reported flares outcome in conditional logistic regression models, using data from all scheduled and flare window e-Questionnaires over 1- year. There will be one model for each of the 10 primary activity categories. Models will include activity categories as time-varying predictors as in **equation 1**, where  $Y$  is the outcome (flare vs. no flare),  $x$  is the activity

exposure (yes vs. no), and  $C$  represents potential time-varying confounders (psychological factors, other activities). The letter  $i$  indicates the  $i^{\text{th}}$  individual ( $i = 1, 2, \dots, n$ ),  $j$  indicates the  $j^{\text{th}}$  time of follow-up ( $j = 1, 2, \dots, n_i$ ) and  $x_{i(j-1)}$  indicates an activity that was performed in the exposure window prior to the  $j^{\text{th}}$  time (either the start of the control window [scheduled e-Questionnaire] or time of flare onset [flare window e-Questionnaire]). As previously noted, the survey methods are such that activity exposure and flare outcome are inherently time-lagged, with exposure preceding outcome.  $\beta_w$  represents the association of activity  $x$  with flare outcome  $Y$  within individuals (the ‘within-individual effect’), or the expected odds of a flare with change in the activity exposure for a given individual. These analyses will yield odds ratios (OR) and 95% confidence intervals for within-individual ‘effects’ of activity triggers on an LBP flare. The initial analytic approach (**Figure 3**) will examine the association between binary activity exposure and binary flare outcome, with explicit adjustment for pain NRS and number of prior flares measured at time= $j-1$ , and time-variant confounders selected based on conceptual importance; *by design*, the case-crossover method uses each person as their own control, accounting for known and unknown confounds that are fixed or relatively stable over time (i.e., age, sex, sociodemographics, medical and LBP history, work-related factors, and underlying psychological predispositions). We will use a Bonferroni-corrected threshold of  $p=0.005$  for each

$$\log \left[ \frac{Pr(Y_{ij} = 1)}{1 - Pr(Y_{ij} = 1)} \right] = \beta_{0i} + \beta_w x_{i(j-1)} + \gamma C_{i(j-1)}, i = 1, 2, \dots, n; j = 1, 2, \dots, n_i \quad (1)$$

[figure not shown]

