\*Analysis includes all scheduled and flare window e-Surveys. Activity exposures over prior 24-hr and 2-hr effect periods, and current flare status, are inherently time-lagged.

primary activity-

flare comparison to account for 10 statistical comparisons (one for each of the 10 activity categories). We will further examine for activity-flare associations after accounting for important relationships based on theory and clinical knowledge, including the following: dose-response relationships; work- specific activity-flare associations; multivariate analyses including other potential confounders (other time-varying activities, depression, PTSD, stress, catastrophizing); potential moderators; different effect-periods of activity exposures (i.e., 24 vs. 2 hours); possible biases (e.g., conscious activity avoidance and carry-over effects); and clinical subgroup analyses (lumbosacral radicular syndrome [LSRS] symptomatic lumbar spinal stenosis [SLSS] diagnosed by a specialist, ascertained by chart review). We will also conduct similar subgroup analyses as secondary analyses, targeting the expanded target population subgroups described above (facet-mediated pain, SIJ-mediated pain, spondylolysis, ascertained by EHR review). We will analyze the reliability and accuracy of these subgroups. Of note, the primary analysis of walking, standing, and sitting will use the ActiGraph data (which are only obtained for the 1st 4 weeks of follow-up); secondary analyses will use the self- reported data for these 3 groups over the entire 1-year follow-up, and will also examine the association between ActiGraph and self-reported data. After these analyses using the binary flare outcome, we will use an analogous approach to examine relationships between activity categories and the secondary (continuous) outcome of NRS LBP intensity, with linear mixed-effects regression. These analyses account for potential biases that might be introduced by participant self-identification of flare status; if no such bias exists, we would expect the direction of effects to be similar to those obtained in the initial analysis of flares.

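### Aim 1's year-long self-report models pool front-loaded scheduled reports with any-time flare reports and name no follow-up-time term, leaving a modest but testable trend bias

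*Combined protocol and SAP*

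**What the plan says.** The Aim 1 model (5.6.2a) is fitted "using data from all scheduled and flare window e-Questionnaires over 1- year". Equation 1 contains a person intercept, the activity in the window before the report, and a vector of time-varying confounders exemplified by psychological factors and other activities. The initial model is run "with explicit adjustment for pain NRS and number of prior flares measured at" the previous time point, plus "time-variant confounders selected based on conceptual importance". Self-matching is credited with handling factors that are fixed or nearly so.

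The two report types follow different clocks. Section 5.5 states: "Scheduled e-questionnaires will be administered 3 times weekly during weeks 1-4, once a week during weeks 5-8, and twice a month from months 2-12". Section 5.2.7 pays "each for scheduled e-Questionnaires (up to 36 for each participant"). Flare-window reports are initiated by participants "if they experience new flares of LBP at any time during the 1-year follow-up period" (5.1).

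For three activities the year-long model is secondary, because "the primary analysis of walking, standing, and sitting will use the ActiGraph data", which covers weeks 1-4 only. Each activity is tested at p=0.005. The bias checks listed in 5.6.2a are activity avoidance and carry-over; a follow-up trend is not among them.

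**The concern.** In a case-crossover analysis the control periods should represent the person's exposure over the time when the cases could arise. Here the control periods come almost wholly from the scheduled reports and over-represent the first two months. Flare-window cases need not follow that pattern. A within-person trend in activity then appears as an activity-flare association even when there is none. Such a trend is not a stable characteristic, so the person-specific intercept cannot absorb it.

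The plan itself gives a reason to expect one: section 5.6.2b says restriction of activity is most likely early in a back-pain episode. If activity rises after enrolment, the bias runs upward, toward calling the activity a trigger. If it falls, the bias runs downward and can hide a trigger.

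The point affects the seven activities whose primary analysis is self-reported, and the secondary year-long analyses of walking, standing and sitting. It does not reach the weeks 1-4 ActiGraph analyses. The power simulation could not have shown it, because by the plan's account the estimates are such that "they use data from scheduled e-Questionnaires only and assume no data from" the flare-window reports (5.6.1).

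**Working it through.** **Schedule.** 3 × 4 = 12 reports in weeks 1-4, 1 × 4 = 4 in weeks 5-8, and 2 × 10 = 20 in the ten months after that. The total of 36 matches the payment cap. (Reading months 2-12 literally as eleven months gives 38.) Share in weeks 1-8: 16/36 = 44%, in 56/365 = 15% of the year.

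**Closed form, true OR 1, activity as the only term.** Assumed activity: 6.8% in weeks 1-4, 12.5% in weeks 5-8, 17.3% later. Also assumed: 9% of scheduled reports in flare, and 8 flare-window reports spread evenly over the year.

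- Control exposure: (12 × 6.8 + 4 × 12.5 + 20 × 17.3)/36 = 13.3%.
- Flare-window exposure: (28 × 6.8 + 28 × 12.5 + 309 × 17.3)/365 = 16.1%.
- Scheduled flares: 0.09 × 36 = 3.24, at 13.3%.
- Case exposure: (3.24 × 13.3 + 8 × 16.1)/11.24 = 15.3%.
- OR = (0.153/0.847)/(0.133/0.867) = 1.18.

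The range is 1.05 (20% scheduled prevalence, 2 flare-window reports) to 1.22 (5%, 12 reports).

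**Simulation with the planned adjustment.** Exact conditional logistic regression on 4,400 people (ten studies of 440), with gamma frailty between persons. On average there were 7.3 flare-window and 3.2 scheduled flares per person (3.9 and 7.1 in the 20% scenario). A flare raised lagged pain by 1.5 points; mean pain was flat or fell 1.5 points over follow-up. The model included prior-flare count and lagged pain. Without these two covariates, the steep uniform scenario gave 1.17, in line with the closed form. The false-positive rate is a normal approximation for n=440, taking p<0.005 as two-sided.

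| Scenario (true OR 1; activity in weeks 1-4, 5-8, later) | OR | False positives |
|---|---|---|
| Steep, 7%, 12%, 17%; flare-window reports uniform | 1.10-1.11 | 17-22% |
| Same, adjusting also for the other nine activities | 1.09-1.10 | 13-17% |
| Moderate, 10%, 14%, 17% | 1.07 | 6% |
| Steep; 20% scheduled flare prevalence, 4 flare-window reports | 1.06 | 4% |
| Steep; daily flare-report rate falling 2 : 1.5 : 1 | 1.07 | 6% |
| Steep; scheduled flare prevalence also falling | 1.05 | 3% |
| Mild, 10%, 11%, 12% | 1.02 | 0.7% |
| Flare timing matched to the schedule | 1.02 | 1% |

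The Monte Carlo SE of the log OR is 0.016-0.018, so 1.02 is about one SE from no bias. As a check on one rate: the SE at n=440 is 0.017 × √10 = 0.054; ln(1.105)/0.054 = 1.86; and P(Z > 2.81 − 1.86) = 17%.

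Adding a follow-up-time spline to the same covariates gave 0.98-1.00 in every scenario. The SE stayed between 0.016 and 0.018 with or without it.

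**Second simulation, different assumptions.** n=440, 12 replicates, 6 flare-window reports per year, 10% of scheduled reports in flare, constant flare rate, pain not modelled. The ORs are for no adjustment, prior-flare count, and prior-flare count plus period term; activity is first period to last.

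- 10% to 15%: 1.06, 1.04, 0.99.
- 5% to 10%: 1.13, 1.09, 1.00.
- 10% to 20%: 1.15, 1.11, 1.02.
- No trend: 1.00 throughout.
- 10% to 15% with a true OR of 1.5: 1.70, 1.66, 1.57. The time term removes part of the excess; the remainder exceeds simulation error (SE 0.012) and is not explained by it.

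In closed form, a falling trend (15% to 10%) gave 0.90-0.94. A 10% to 15% rise with the flare rate doubled early gave only 1.00-1.05.

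**The case against.** Several points can fairly be made for the plan.

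- **The term may already be allowed for.** Figure 3, which sets out the initial approach, is not readable in the available text. The clause on conceptually important time-variant confounders could admit follow-up time, and 5.6.2 calls all analyses preliminary. Prior-flare count can only rise with time and is a partial proxy. All true, but no readable text names the term, and in simulation the prior-flare count removed only about a quarter to two-fifths of the bias.
- **The trend is assumed.** Enrolment is not episode onset: mailed recruitment follows the visit, and eligibility does not require a new episode. Flares may cluster early, and the payment scale, which falls as flare reports accumulate, favours early reporting. This stands as a limit on size. The table shows how far the bias then shrinks.
- **The false-positive rates may be high.** Section 3.0 confines the main aims to the original target population, so the primary sample may be below 440. At OR 1.105 the rate falls from 17% to about 10% at n=300 and 7% at n=220 (both sizes assumed). The psychological covariates, which might track early restriction, were not simulated.
- **The bias lies below what the plan calls meaningful.** Section 5.6.1 looks for ORs of 1.5-2.0. That stands, so no large false trigger would be created. But the primary comparisons are judged at p=0.005, and section 5.6.3 intends to weigh even small increases in flares against long-term benefit.

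**Conclusion.** The concern holds. The model as described samples cases and controls on different time scales and names nothing to correct for it. Under a moderate or steep within-person rise in activity and a true OR of 1, the simulations put the estimate at about 1.04 to 1.11 after the planned adjustment. A third run, adjusting for prior flares only, extended this to 1.16; its estimates were about 0.99 under a mild trend and 0.97-1.04 with a period term (Monte Carlo SE 0.02-0.03). False positives run from near nominal to roughly a fifth.

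These sizes depend on assumed trends, flare counts and flare timing. With no activity trend there is no bias, and when flare timing follows the schedule any bias is within simulation error. Confidence in the mechanism is high; confidence in the size is moderate. The plan should be changed, but the defect does not threaten the study.

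**What to change.** State in 5.6.2a that the year-long self-report models include time since enrolment within equation 1: either days as a linear spline with knots at weeks 4 and 8 (3 degrees of freedom) or period categories for weeks 1-4, weeks 5-8 and later (2 degrees of freedom). Keep the planned pain and prior-flare adjustment. Reporting each estimate with and without the time term would show whether the trend mattered.

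Add a sensitivity analysis restricted to scheduled e-Questionnaires, with the same time term. Treat it as supportive only: when scheduled flare prevalence itself fell, the simulated scheduled-only OR under no effect was 0.91 without the time term and 0.95 with it (SE 0.03), so a small disagreement with the pooled result would not be decisive.

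The cost is a sentence or two in the plan. The timing of each report is already recorded, no new data are needed, and precision is essentially unaffected.

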**5.6.2b. Aim 2 analyses:** We will examine associations between the frequency of activity during scheduled e-Questionnaires (% of periods during which each of the 10 primary activity categories were reported over the 1st 4 weeks of follow-up), and the outcome of long-term LBP-related functional limitations at 12 months as reflected by the RMDQ, using a Bonferroni-corrected threshold of p=0.005 (**Figure 4**). Activity over the 1st 4 weeks is the exposure of interest for the Aim 2 analysis because activity restriction is most expected early in an episode of LBP, and because of our previously-stated reasoning that early changes in activity may be particularly important in determining long-term/overall activity-function relationships. The percentage of periods with each activity category over the 1st 4 weeks will be calculated from self-reported activity information and ActiGraph output. The main multivariate model for each activity category will explicitly adjust for a range of potential confounders based on prior knowledge and conceptual rationale, including baseline RMDQ score, and all psychological predictors and other baseline covariates. We will then conduct secondary analyses analogous to that done for Aim 1 to examine activity-1-year-RMDQ associations after accounting for important relationships based on theory and prior knowledge: potential moderation by baseline employment status, compensation status, or job satisfaction; potential moderation by analgesic use over the first 4 weeks of follow-up; sensitivity analyses contrasting associations with cumulative activity exposure early (weeks 1-2) vs. late (weeks 3-4 or weeks 5-8).

during follow-up; and clinical subgroup analyses (LSRS and SLSS subgroups). We will use the same approach for the secondary outcomes of LBP intensity, lost work productivity, quality of life, and analgesic use at 1-years.

Analyses for Aims 1 and 2 will use VA administrative data to weight the sample of participants back to represent the target population of Veterans with back pain (including those who did not respond to the study).

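### Adjusting the Aim 1 conditional model for prior flares, with no stated time term, biases the odds ratio of any activity that trends over follow-up if the count is cumulative

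*Combined protocol and SAP*

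**What the plan says.** Section 5.6.2 a analyses the "participant-reported flares outcome in conditional logistic regression models", with one model per activity category, "using data from all scheduled and flare window e-Questionnaires over 1- year". The initial approach, which carries the 0.005 threshold, has "explicit adjustment for pain NRS and number of prior flares measured at" time j-1. A count that was constant for a person would cancel out of a conditional model, so this one must change over time. No look-back window is stated.

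In equation 1 the covariate term "represents potential time-varying confounders (psychological factors, other activities"). Neither the equation nor the text names time since enrolment. The text also allows further time-varying confounders, chosen on conceptual grounds. Figure 3, which illustrates the approach, was not visible in the copy reviewed.

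Section 5.6.2b, when justifying the Aim 2 exposure window, says that "activity restriction is most expected early in an episode of LBP". The plan therefore expects activity to change with time, at least early in an episode.

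**The concern.** Conditional logistic regression fixes each person's number of flares and asks which records they fell on, treating the covariates as given. A running count of earlier flares is not given: it is a function of the outcomes being ordered. It can only rise, and it rises only after a flare.

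The fitted coefficient of the count is therefore pulled below zero even when past flares have no effect. Because the count grows over follow-up, a negative coefficient tells the model that later records carry lower risk. If flares are in truth as frequent late as early, any covariate that is more common late must make up the difference. An activity that rises looks harmful and an activity that falls looks protective.

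At stake is the primary odds ratio for each activity with a within-person trend. Those odds ratios feed the tables of risk estimates described in section 5.6.3.

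**Working it through.** **The plan's own figures.** 440/(1 - 0.40) = 733, against 730 planned. 0.05/10 = 0.005, which matches the threshold described as "Bonferroni-corrected for 10 activity groups". Section 5.6.1 claims about 90% "power to detect ORs of 1.5 for activity frequencies" near 10%, and "80% power to detect OR=1.6 at activity frequency=5%, and 80% power for OR= 1.81 given activity frequencies as low as 3" per cent. No flare rate is given, so these powers cannot be reproduced directly. The number of informative flares they imply can be derived, taking the test as two-sided:

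E = (z[0.9975] + z[power])² / (ln(OR)² × p(1 - p))

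- OR 1.5, p = 0.10, power 90%: (2.807 + 1.282)² / (0.1644 × 0.09) = 1130
- OR 1.6, p = 0.05, power 80%: (2.807 + 0.842)² / (0.2209 × 0.0475) = 1269
- OR 1.81, p = 0.03, power 80%: (2.807 + 0.842)² / (0.3520 × 0.0291) = 1300

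Divided by 440, this is 2.6 to 3.0 flares per person. Over 36 scheduled records (section 5.2.7) that is about 8% of records, which was used as the base-case flare rate.

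**Why the bias is structural.** Take a person with T records and one flare at record k, and leave activity aside. Records 1 to k have count 0 and later records have count 1. The likelihood contribution is 1/(k + (T - k)e^γ), where γ is the coefficient of the count. For every k < T this increases as γ falls, whatever the truth. For k = T it contains no γ. With T = 2 and activity included, the flare-first person contributes 1/(1 + exp(γ + β(x2 - x1))), and the flare-second person says nothing about γ. People with several flares keep the estimate finite, but the pull remains downward.

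**Size.** Exact conditional likelihood, 440 people, 36 records, random flare intercept with SD 1, no true effect of past flares, 150 replicates per row. Brackets give coverage of the 95% interval.

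| Activity over follow-up | Flare rate | True OR | No count, no time | Count, no time | OR of the count |
|---|---|---|---|---|---|
| Flat 10% | 8% | 1.50 | 1.49 (96%) | 1.50 (96%) | 0.89 |
| Rising 5% to 25% | 8% | 1.50 | 1.51 (93%) | 1.67 (71%) | 0.89 |
| Falling 25% to 5% | 8% | 1.50 | 1.49 (97%) | 1.36 (81%) | 0.89 |
| Rising 5% to 25% | 8% | 1.00 | 1.01 (96%) | 1.12 (75%) | 0.89 |
| Rising 8% to 12% | 8% | 1.50 | 1.47 (95%) | 1.51 (95%) | 0.89 |
| Rising 5% to 25% | 20% | 1.50 | 1.49 (95%) | 1.59 (85%) | 0.96 |

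- In the null row, rejection at 0.005 was 10 of 150 (6.7%, 95% CI 3.2 to 11.9%) with the count, against 1.3% without it.
- In the falling row, power was 79% with the count, against 98% without it.
- Two further sets of runs of the 5% to 25% null case gave activity ORs of 1.11 (100 replicates, coverage 79%, 3 rejections) and 1.10 (60 replicates, coverage 78%, rejection 6.7%), with the count's own OR at 0.88 in both.
- At true 1.5 they gave 1.65 for rising activity (100 replicates) and 1.38 for falling activity (60 replicates).

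**With time in the model.**

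- Time in place of the count: 1.00 under the null (coverage 97%) and 1.50 at true 1.5 (coverage 94%).
- Count plus time: 1.01 under the null.
- If past flares do raise risk (log-OR 0.05 each, true activity OR 1.5, rising 5% to 25%): 1.64 with the count alone, 1.56 with neither, 1.48 with count plus linear time. A separate 60-replicate run of the case in which past flares raise risk gave 1.52 with time only and 1.50 with both.

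**The case against.** The case against rests on five points.

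1. **The count is not defined.** A cumulative count is a reading. If flare status at the previous record were meant, runs with a 5% to 25% rise gave an activity OR of 0.99 and no rejections in 100. This stands, and it is why the definition belongs in the fix.

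2. **The trend is assumed.** The sentence in 5.6.2b concerns the early part of an episode and gives no size. Table 1 does not require a new episode at enrolment. If restriction resolves with a 14-day time constant, the null OR is 1.02 (10% to 20%) or 1.05 (5% to 25%). This stands.

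3. **Recovery may lower flares too.** With activity rising 5% to 25% and flare odds halving, the null OR was 1.06 with the count (0 of 100 rejected) and 0.90 with neither count nor time (6% rejected). With flare odds falling to a third it was 1.04, against 0.84 (19% rejected). Here the count serves as a partial proxy for time. This stands, but it argues for modelling time and against simply deleting the count.

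4. **Time might be in the model already.** Figure 3 is not visible and the open list of confounders could include time. So one can say only that the readable text names no time term.

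5. **Pain NRS at j-1 was not simulated.** It could absorb part of a trend.

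The plan's description of its analyses as provisional, and its later checks on activity avoidance and carry-over, do not address a covariate derived from the outcome.

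A reader might infer that the model generally makes inert activities look like triggers, with false-positive rates of 8 to 14%. The documents do not support that. The direction follows the activity trend, and those rates arise only when activity climbs to 36% or 40% with no change in flares, whereas section 5.6.1 expects frequencies of 5 to 25%.

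**Conclusion.** The concern holds in a conditional form. If the prior-flare count is cumulative and no time term enters, the primary activity OR is biased whenever that activity trends within person, in the direction of the trend.

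- **Swing across the plan's 5 to 25% range:** an error of about 10%, with coverage of about 71 to 81%.
- **Mild or early-resolving trends, or flares that also decline:** about 2 to 6%.
- **Stable activity:** none. Activity that merely drops after a flare, with no trend, adds none either (1.53 with the count, 1.54 without).
- **Walking, standing and sitting:** their primary analysis uses ActiGraph data from the first 4 weeks, about 3 × 4 = 12 scheduled records. The error may be larger there: null ORs were 1.12 to 1.19, with 2 to 4% rejected, when flares had no trend.

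These sizes rest on assumed flare rates, trends and random-effect SDs, on scheduled records only, and on 60 to 150 replicates per scenario. The planned 730 is not affected.

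A reader might also conclude that the count must be removed. The results do not require that: the term for time is what removes the bias, with or without the count.

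**What to change.** In section 5.6.2 a:

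- Add a flexible term for time since enrolment, for example a spline in study week, to the primary model of every activity, and show it in equation 1.
- Define the number of prior flares: which questionnaires count and over what look-back window.
- State that a cumulative count will not be used without the time term.
- Report each activity OR with and without the count as a sensitivity analysis, keeping time in both.

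The cost is a few degrees of freedom and about one line of wording. No new data are needed, since the questionnaire schedule and flare reports already place each record in time.
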